Safety Evaluations	Consent in advance of participation participation is being waived because informing participants in advance would introduce bias and compromise the validity of the study. In accordance with the ethical principles and policies outlined by the Tri-Council Policy Statement (TCPS2) related to waiving consent, participants will be debriefed at the end of the trial and given the opportunity to withdraw their data if they choose.			

Statistical Analysis	All analyses will follow the intention-to-treat principle. Descriptive statistics will be used to summarize participant characteristics. The primary analysis will compare screening attendance between arms using absolute and relative differences; chi-squared test or Fisher's exact tests will assess significance. Logistic regression will be used to explore moderation effects across subgroups (age, gender/sex, preferred language, prior DRS attendance, and Forward Sortation Area (FSA).			
Data and Safety Monitoring Plan	The Principal Investigator ([name]) and his delegate ([name]) will be responsible for data quality management and ongoing assessment of the study conduct.			

Schematic of Study Design

Screening

Day 0

Total N =330

Randomly select eligible participants (N=330) from CDEPO database. Randomize eligible participants to two conditions (n = 165 per condition), divided into two waves. Consent waived.

Active Intervention Period

Days 1

Distribute first wave of electronic reminders to intervention group.

Track number of reminders sent, appointments made, and appointments attended, by intervention condition. Debrief appointment attendees

Day 30

Distribute second wave of electronic reminders to intervention group.

Track number of reminders sent, appointments made, and appointments attended, by intervention condition. Debrief appointment attendees.

Active intervention period concludes

Day 90

Conclude active intervention period – Wave 1 intervention and control groups

Day 120

Conclude active intervention period – Wave 2 intervention and control groups

Post intervention debriefing and reminders

Day 121 (or next business day)

Debriefing information distributed to wave 1 participants who have not yet been debriefed.

Reminder to attend DRS distributed to control group participants in wave 1.

[figure not shown]
Day 151 (or next business day)

Debriefing information distributed to wave 2 participants who have not yet been debriefed.

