increase DRS	regularly have their eyes	at CCHC.	observation
attendance in	screened.		period.
participants living			
with diabetes,			
compared to not			
sending a			
reminder.			

Secondary Objectives

Objective Brief Description/Justification o Outcome Measure		Outcome Measured By	Time Frame
Assess whether linguistically tailored reminders incorporating BCTs increase DRS appointment bookings in participants living with diabetes, compared to not sending a reminder.	Not all participants who book an appointment may attend an appointment. Assessing appointment booking in addition to appointment attendance is important to understand if the intervention is effective in both promoting appointment booking and attendance.	The proportion of participants in each condition who book a DRS appointment at CCHC.	Assessed at the conclusion of the intervention/ observation period.
To examine whether the effect of the intervention on DRS attendance is moderated by participant characteristics, including age, gender/sex, preferred language, prior DRS attendance, and Forward Sortation Area (FSA).	Participant characteristics are likely to influence appointment booking and attendance.	Interaction effects between intervention group and subgroup variables (age, gender/sex, preferred language, prior DRS attendance, FSA) in a logistic regression model predicting DRS attendance.	Assessed at the conclusion of the active intervention period (4 months after first wave of reminders is sent).

Study Design and Endpoints

Description of Study Design

This study is a two-arm randomized controlled trial (RCT) evaluating the effectiveness of a linguistically tailored, BCT based electronic reminder in promoting diabetic retinopathy screening (DRS) attendance. Participants will be randomly assigned to one of two study arms:

- Control group (no reminder)
- Reminder Group (receives reminder incorporating knowledge, social and goal based BCTS).

Participants will be drawn from the Community Diabetes Education Program of Ottawa (CDEPO), registered at Centretown Community Health Centre (CCHC). To avoid overloading clinic resources, reminders will be sent in two waves. Control group participants will be matched to these waves based on distribution timing.

Duration of Study Participation

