Participants may withdraw from the study at any time from when they are debriefed about their participation until the study findings are submitted for publication in a peer reviewed journal. No data will be transferred to the research team at OHRI until 2 weeks after all participants have been debriefed, providing ample opportunity for participants to withdraw from the study prior to their data being shared. During this period, data collection by CCHC staff may continue to ensure that any late-stage appointments or withdrawal requests are captured. Requests to withdraw from the study will be made to, and documented by, CCHC staff. When participants withdraw from the study prior to data being shared with the OHRI study team, a note will be placed in the Trial Tracker in the individual's EMR, and the OHRI study team will only receive a summary of the number of participants withdrawn in each condition. If a participant withdraws after data has been shared with the OHRI study team, members of the CCHC team will notify the researchers of the individuals de-identified record number and the individual's data will be deleted and excluded from subsequent analysis.

Study Assessments and Procedures

[figure not shown]
Intervention Preparation Phase

An initial version of the electronic reminder has been developed in English. The research team will collaborate with community partners to tailor the reminder ensuring they are culturally and linguistically appropriate for four linguistic groups that are representative of the linguistic diversity of CCHC clients in Ottawa: Arabic, English, French, Mandarin speaking people. Community partners will include people who are members of these communities, including multi-cultural health navigators or health care providers.

The reminder will then be translated into Arabic, French, and Mandarin with assistance from multilingual collaborators. Prior to launching the intervention, reminder distribution procedures will be tested using mock participant files to confirm the correct delivery and functionality of associated links.

Intervention Phase

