Reminders will be distributed using the OCEAN secure messaging system integrated with the CCHC electronic medical record (EMR). The reminder will include a unique link to a landing page, where participants can select their preferred language (English, French, Arabic, or Mandarin) to view the tailored content. A schematic of the intervention experience follows, along with a copy of the landing page.

To manage clinic capacity, reminders will be distributed in two waves, each consisting of 80 (+1) participants per condition. Wave 1 participants will receive reminders on Day 1 and will be tracked for 90 days. Wave 2 participants will receive reminders on Day 30 and will be tracked for 90 days (Day 120). Control participants will be matched to these waves to ensure comparable observation periods.

ARM	Wave 1	Wave 2	TOTAL
1 (Control)	83	82	165
2 (Intervention)	83	82	165
TOTAL	166	164	330

Wave	Group	Day 1	Days 1-	Day 30	Days 30-	Day	Day	Day 121	Day 151
			29		120	90	120		
Wave	INTERVENTION	Send	Track bo	rack booking and attendance			Debrief		
1		reminder							
	CONTROL	No	Track booking and attendance				Debrief and DRS		
		reminder						reminder	
Wave	INTERVENTION			Send	Track booking and		t		Debrief
2				reminder	attendance				
	CONTROL			No Track booking and		t		Debrief and DRS	
				reminder	_				reminder

Participant Contact and Booking Process

[figure not shown]
Participants will be able to contact DESO (Diabetes Eye Screening Ottawa) at CCHC via phone, routine CCHC workflow:

- 1. DESO staff will initiate the booking process by faxing a referral to the participant's primary care provider.
- 2. Once the referral is received, the administrator will contact the participant to schedule an appointment.
- 3. If an interpreter is required, one will be arranged unless declined by the participant.

Debriefing Procedures

Debriefing procedures are as follows (and presented in the figure below):

- In-person debriefing: Participants attending a DRS appointment will receive a verbal debrief upon arrival at CCHC.
- Electronic debriefing: Participants who do not attend an appointment will receive a written debrief via the OCEAN EMR system.
- Debriefing materials will explain the study's purpose, data usage, and instructions on how participants can withdraw their data if desired.

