- No data will be transferred to the research team until at least two weeks after all participants have been debriefed. Until then, follow-up data (e.g., booking or attendance status, withdrawal requests) may continue to be documented by CCHC staff to ensure complete and accurate records.

Study Procedures / Evaluations

Procedures/Evaluations

When a participant books or attends a DRS appointment, DESO staff will update the DESO Reminder Trial Tracker, which will be maintained within the EMR system (see example below).

Example Remine	der Trial Tracker:
Reminder Received?	Appointment with DESO Booked
Client Contacted DESO Date (DD/MM/YY)	□ Yes □ No
Client Contact Type	□ In process
 Phone call 	If appointment booked- interpretation services booked?
 Email 	□ Yes
 Self-Referral Form Online 	□ No
 No contact (default) 	Appointment Attended?
Language Spoken by Client	□ Yes □ No show
Age of client in years Forward Sortation Area (first 3 digits of postal code):	Retinopathy Status:
Has client had a DRS exam before?	Contacted to withdraw data from study?
□ Yes	 No (default)
□ No	 Yes (if yes, DO NOT include this participant's data
If yes, approximately what year was last DRS exam	in the data pull)

After the debriefing period, CCHC staff will extract de-identified trial data and transfer it as a CSV file to a secure OHRI SharePoint folder accessible only to the approved research team. Variables shared with the research team will include all information logged in the Reminder Trial Tracker. The research team will also be advised of the number of participant withdrawals from each group.

Pt ID	Arm	Wave	Contact Clinic (Y/N)	Book Appointm ent (Y/N)	Attend Appoint ment (Y/N)	Age	Gender	Sex	Prior DRS	Spoken Langua ge	DR Status	FSA
1												
2												

Example csv data file.

[figure not shown]
Control of Bias and Confounding

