interpretation booked,	arm.		secure SharePoint	
appointment attended,			file between OHRI	
retinopathy detected, spoken			and CCHC.	
language, age, FSA, prior DRS				
attendance.				
Web analytics (basic metrics	To describe website use	Google	Data will be	JP. JO,
including number of website	as this is the platform for	analytics or	exported to a	MD. EG
visits, duration of website	the intervention.	website	secure SharePoint	
visit/ session. clicks on		developer	by the Site Owner	
secondary link) No web		analytics	(CCHC)	
identifiers (e.g., IP address				
are to be collected)				

Data Collection and Management Responsibilities

De-identified quantitative data will be collected as part of the reminder evaluation. Only the variables specified in the Reminder Trial Tracker will be collected. Final data collection at the site level may continue beyond the active intervention period to allow documentation of any appointments or withdrawal requests that occur before participants are debriefed. This data will be stored in CSV format on a secure OHRI SharePoint site with access limited to study team members responsible for the analysis.

Data Sharing and Reuse

Identifiable data will not be shared. Summaries of analysed data may be shared with relevant partners (i.e., CCHC, Diabetes Action Canada, OHRI research team meetings) prior to the submission of final reports or manuscripts.

De-identified and cleaned datasets, with all direct and indirect identifiers removed, may be uploaded to a secure open-access repository such as the Federated Research Data Repository (FRDR). FRDR is a national platform designed to support the sharing and preservation of Canadian research data.

Study Records Retention

Raw data, data summaries and analyzed data will be stored in a secure file within SharePoint that can only be accessed restricted to members of the study team. Should a researcher leave before the end of the data retention (i.e., 10 years post study completion), they will be removed from the shared folder. JP is responsible for any questions during the retention period.

Protocol Deviations

Any need to deviate from the approved protocol will be reported to the REB and no changes will be made to the approved protocol without informing the REB.

Knowledge Translation

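### Bookings and attendances are recorded without dates and may be collected past the 90-day window, so controls prompted by their deferred reminder could count in the primary comparison

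*Protocol*

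**What the plan says.** **Intended window.** Under Intervention Phase: "Wave 1 participants will receive reminders on Day 1 and will be tracked for 90 days" and "Wave 2 participants will receive reminders on Day 30 and will be tracked for 90 days (Day 120". Controls are matched to the waves so that observation is comparable. The objectives tables assess attendance and booking at the end of the intervention or observation period.

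**Control reminder.** The schematic places this at Day 121: "Reminder to attend DRS distributed to control group participants in wave 1". Wave 2 controls get theirs on "Day 151 (or next business day"). In each wave the debrief of those not yet debriefed is sent on the same day.

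**How long data are collected.** Three statements differ:
- The synopsis (Study Phases) says collection, with attendance status named, will go on until all participants are debriefed. That is Day 151.
- Handling of Participant Withdrawals or Termination holds back data transfer until two weeks after the last debrief and adds: "During this period, data collection by CCHC staff may continue to ensure that any late-stage appointments or withdrawal requests are captured". Debriefing Procedures repeats this: "Until then, follow-up data (e.g., booking or attendance status, withdrawal requests) may continue to be documented by CCHC staff".
- Data Collection and Management Responsibilities says collection "may continue beyond the active intervention period to allow documentation of any appointments or withdrawal requests that occur before participants are debriefed".

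**What is recorded.** The example Trial Tracker has status boxes for booking and attendance and one event date, the date the client contacted the screening service. The example CSV reduces contact, booking and attendance to Y/N. The data management section says that only tracker variables will be collected. Statistical Methods compares two proportions and gives no day cut-off.

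**The concern.** The randomised contrast, reminder against no reminder, exists only until controls are reminded. Two of the three collection statements allow attendance status to be updated after that day, and the data file has no date by which a later attendance could be removed. A wave 1 control who attends on Day 140 after the Day 121 reminder has the same attendance entry as one who attends unprompted on Day 40.

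Such events would raise the control proportion for attendance (primary) and booking (secondary), pulling both differences toward zero. At the planned 3% only about 5 control attendances are expected (0.03 × 165 = 4.95), so a few extra ones matter. An analysis plan written later could define a cut-off but could not apply it to dates that were never captured. That makes this a protocol matter.

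**Working it through.** **1. Timeline**
- Earliest transfer: Day 151 + 14 = Day 165.
- Reminded control time if collection runs to transfer: wave 1, 165 − 121 = 44 days; wave 2, 165 − 151 = 14 days.
- Reminded control time under the synopsis text (to Day 151): wave 1, 151 − 121 = 30 days; wave 2, none.
- Under the data management text, read participant by participant: none, because debrief and control reminder fall on the same day.

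**2. The plan's own figure**

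Inputs from Total Number of Participants and Sites: 0.03 v 0.13, two-sided 5%, pooled Z-test, 80% power.

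n per arm = [1.960 √(2 × 0.08 × 0.92) + 0.842 √(0.03 × 0.97 + 0.13 × 0.87)]² / 0.10² = 114.4, so 115 per arm and 230 in total.

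230 / (1 − 0.30) = 329, which matches 330 under the 30% attrition in Sample Size Determination. The 10% given in the other section yields 256. That conflict is a separate matter. The power figures below use all 165 per arm.

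**3. Power without late control events**

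Power = Φ[(Δ − 1.960 × SE₀) / SE₁], with SE₀ pooled and SE₁ unpooled.

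For 0.03 v 0.13: SE₀ = 0.02987, SE₁ = 0.02936, (0.10 − 1.960 × 0.02987) / 0.02936 = 1.412, power 92%.

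**4. Power with late control events**

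The documents give no accrual curve. Assumptions: the control reminder has the full 10-point effect, accruing linearly over 90 days; the intervention arm stays at 13%; wave sizes are 83 and 82 per arm, as in the protocol table.

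Added control rate = 0.10 × (83 × d₁/90 + 82 × d₂/90) / 165, where d₁ and d₂ are reminded days in waves 1 and 2, less any lag (not below zero).

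Day 165, no lag: 0.10 × (83 × 44/90 + 82 × 14/90) = 5.3 extra attendances, or 3.2 points. Control rate 6.2%, difference 6.8 points, SE₀ = 0.03246, SE₁ = 0.03224, power 55%.

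An attendance needs a faxed referral, a call-back and an appointment. The protocol gives no duration for these steps, so the lag is also an assumption:

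| Collection to | Lag (days) | d₁, d₂ | Control rate | Difference (points) | Power |
|---|---|---|---|---|---|
| Day 165 | 0 | 44, 14 | 6.2% | 6.8 | 55% |
| Day 165 | 14 | 30, 0 | 4.7% | 8.3 | 76% |
| Day 165 | 21 | 23, 0 | 4.3% | 8.7 | 81% |
| Day 165 | 30 | 14, 0 | 3.8% | 9.2 | 86% |
| Day 151 | 0 | 30, 0 | 4.7% | 8.3 | 76% |
| Day 151 | 14 | 16, 0 | 3.9% | 9.1 | 85% |
| Day 151 | 21 | 9, 0 | 3.5% | 9.5 | 88% |
| Day 151 | 30 | 0, 0 | 3.0% | 10.0 | 92% |

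Without a time model: if 10%, 25% or 50% of the effect appears in controls before extraction, power is 84%, 65% or 32%.

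**5. Can the contact date repair it?**

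In part. Data Management Plan lists it among the variables used by the research team. It could flag a control whose first contact came after the reminder, and wave 2 contacts before Day 30. It cannot date the booking or the attendance: a contact on Day 80 may lead to an attendance on either side of Day 90. No rule in the protocol uses it.

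**The case against.** The strongest reply is that the window is already stated. Each wave is tracked for 90 days, outcomes are assessed when that period ends, and later collection can be read as site record-keeping; Duration of Study Participation gives its purpose as documenting participation status and withdrawal requests. The data management text, read per participant, would exclude every attendance prompted by the control reminder. A statistical analysis plan may also set the cut-off. The intent is indeed clear. What remains is that the synopsis and the two transfer passages name attendance or appointments as things to go on recording, and that no cut-off can be applied to undated fields.

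A reader might go further in four ways that the documents do not support:
- *That attendance is definitely collected to Day 165.* Days 151 to 165 are permitted, not required. Only the synopsis text, to Day 151, is mandatory, and it exposes wave 1 controls alone.
- *That the moderation time frame is a rival window.* "Assessed at the conclusion of the active intervention period (4 months after first wave of reminders is sent") is a time of assessment, at about Day 120.
- *That late control events could not be detected at all.* The contact date would flag some of them.
- *That power falls to 55%.* That needs the latest collection date, no referral lag and a full 10-point effect. The control message is not said to be the tailored version, and intervention non-attenders are debriefed on the same days, which could prompt some of them too.

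Unequal follow-up between waves would not by itself bias the arm comparison, since each wave has equal numbers per arm. The bias described here runs toward no effect and would not favour the intervention.

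**Conclusion.** The point holds as a gap between a stated window and data that cannot enforce it. Control attendances and bookings prompted by the deferred reminder could be counted, because the collection statements disagree and neither event is dated. The direction is toward no effect; the size cannot be known from the protocol. Under the assumptions shown, the loss ranges from nothing (Day 151, 30-day lag) to a fall in power from 92% to 55% (Day 165, no lag), with most lagged scenarios between 76% and 88%. It should be settled before the first reminders go out, because event dates are easy to record as they occur and the planned extract could not supply them afterwards.

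**What to change.** 1. Add booking date and attendance date to the Trial Tracker and to the CSV sent to the research team.
2. State one endpoint rule: primary, booking and moderation events count only if they fall within the wave's own 90-day window, identically in both arms. Write it as days since the wave's start, because Day 1 to 90 and Day 30 to 120 differ by one day (89 and 90 days elapsed).
3. Report later events separately, outside the between-arm comparison. A sensitivity analysis may count attendance up to the day before the control reminder.
4. Reconcile the synopsis (Study Phases), Handling of Participant Withdrawals or Termination, Debriefing Procedures, and Data Collection and Management Responsibilities with this rule. Late site collection can continue for withdrawals and records.

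Cost: two data fields, one endpoint sentence and matching edits to four passages. No extra participants or contacts are needed.

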All analyses will be conducted according to the intention to treat principle. Descriptive statistics (mean and SD for continuous variables or median and IQR for skewed distributions, and frequency and proportion for categorical variables) will be used to summarize participant characteristics in each arm. For the primary analysis of the primary outcome, we will compare screening attendance between the arms using absolute and relative difference between two proportions with 95% confidence intervals and assess the statistical significance of the difference using a chi-squared test. If the large-sample assumptions are not met, Fisher's exact test will be used. Statistical significance will be assessed at the 5% level. A similar statistical approach will be used for secondary outcomes. For the final objective of assessing effect modification, we will use logistic regression analysis with the treatment arm, effect modifier and the interaction between treatment arm and effect modifier in the model. Least square mean differences from the model will be used to compare the outcome differences between the subgroup variables: 1) Age, 2) Gender/Sex 3) Preferred Language, 4) Prior DRS Record 5) FSA (Forward Sortation Area).

Source Documents and Access to Source Data / Documents

Access to study records will be limited to REB-approved members of the study team. The PI will permit study-related monitoring, audits, and inspections by the REB and/or OHRI and compliance and Version date: 04/06/2025

quality assurance groups of all study related documents (e.g. source documents, data collection instruments, study data etc.). The PI will ensure the capability for inspections of applicable study-related facilities (e.g. pharmacy, diagnostic laboratory, etc.). Please see the data management plan for more information about data access.

Study Oversight

The study will be overseen by the primary investigator, ([name]) and his delegate ([name]) who will ensure data safety protocols are in place and followed by OHRI and CCHC site data handlers. Data safety during reminder testing phase involves the protection of CCHC client identities when sharing data. No identifying information (i.e., name, health card number, address, phone number or email address) will ever be sent to the OHRI team. If a breach were to occur, the study would stop until the breach was resolved and then restart once there is no question of a second breach.

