This design poses minimal risk to participants. All individuals included have previously consented to receive virtual communications—including appointment reminders and provider messages—from Centretown Community Health Centre (CCHC). The reminder used in this study aligns with these routine communications and does not introduce undue influence or burden.

Debriefing will be provided to all participants after the observation period, either in person (if attending a DRS appointment) or via email (if they do not attend). This post-trial communication satisfies TCPS 2 requirements for appropriate safeguards when consent is waived.

Overall, the waiver is justified on methodological, ethical, and practical grounds, with a favourable balance of potential benefits to risks.

Consent / Assent and Other Informational Documents Provided to Participants

Debriefing forms describing in detail the study intervention/observations, study procedures, and risks are given to the participant and is submitted with this protocol:

Debriefing Form

- Participants who attend a DRS appointment during the active intervention period will be debriefed in person by CCHC staff before screening. They will receive the debriefing form and have the opportunity to ask questions or withdraw from the study at that time.
- Participants who do not attend a DRS appointment will be debriefed in writing. The debriefing form will be sent via the OCEAN EMR using the same method as the reminder distribution.
- CCHC staff will document debriefing in each participant's EMR and record any withdrawal requests accordingly.

Research Data Management

Data Management Plan

The following OHRI researchers will have access to the data JP (Principal Investigator), MD, EG, JO. The primary contact/ person responsible for answering any questions about or managing access to the data is [name].

Type of Data	Purpose	Data	Data Storage	Accessible
		Capture		by
		Systems		
De-identified clinical and	To describe sample and	Electronic	Once exported	JP. JO,
appointment attendance data	observe patterns in	Medical	from the EMR into	MD. EG.
including variables from the	appointment attendance	Record at	Excel by the data	MT. BY
in-chart trial tracker:	by sociodemographic	CCHC	manager at the	
intervention condition, date	variables and to answer		CCHC, file will	
of contact, type of contact,	research question of		locked for changes	
appointment booked,	attendance to DRS per		and be shared to a	

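### Analyses are labelled intention-to-treat, but withdrawn participants are removed after their attendance is known, through a withdrawal offer whose form and timing depend on attendance

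*Protocol*

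**What the plan says.** **Analysis principle.** The Synopsis (Statistical Analysis) and the Statistical Methods section both commit to intention to treat without qualification: "All analyses will be conducted according to the intention to treat principle". The primary comparison is the absolute and relative difference in attendance proportions.

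**What happens to withdrawn data.** Consent is waived, and Handling of Participant Withdrawals or Termination opens the withdrawal period at debriefing.
- Before data transfer: the Trial Tracker (Procedures/Evaluations) instructs, for a withdrawal request, "if yes, DO NOT include this participant's data" in the extract. The handling section adds that "the OHRI study team will only receive a summary of the number of participants withdrawn in each condition".
- After transfer: "the individual's data will be deleted and excluded from subsequent analysis".

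**How withdrawal is offered.** The Debriefing Form section sets two routes.
- Attendees: "Participants who attend a DRS appointment during the active intervention period will be debriefed in person by CCHC staff before screening". It continues: "They will receive the debriefing form and have the opportunity to ask questions or withdraw from the study at that time".
- Others: "Participants who do not attend a DRS appointment will be debriefed in writing", through OCEAN. The Schematic of Study Design places this on Day 121 for wave 1 ("Debriefing information distributed to wave 1 participants who have not yet been debriefed") and on Day 151 for wave 2, after each wave's 90-day tracking has ended.

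**The concern.** Intention to treat means that everyone randomised is analysed in the assigned arm. Here some randomised participants leave both numerator and denominator after their outcome is known, and nothing in the protocol reconciles the two rules.

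The removals may also not be random with respect to the outcome. Attendance, the primary outcome, decides whether a person is asked in person by clinic staff or receives a message weeks or months later. A difference in offer can produce a difference in uptake. Few attendees are expected, so each one removed counts. The trial could report as intention-to-treat an estimate that has been shifted by who chose to withdraw. For withdrawals before transfer, the analysts could not tell, because they see only a count per arm.

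**Working it through.** **Inputs.** From Total Number of Participants and Sites: 3% versus 13% attendance, 165 per arm, two-sided 5% pooled Z-test, 80% power. Withdrawal rates are not in the protocol; every rate below is an assumption.

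**1. The plan's own sample size.** n per arm = [1.96·√(2·0.08·0.92) + 0.8416·√(0.03·0.97 + 0.13·0.87)]² / 0.10² = (0.752 + 0.317)² / 0.01 ≈ 114.4, so 115 per arm and 230 in total. Dividing by (1 − 0.30) gives 329, which matches 330. The 10% attrition in the same section would give 256; the 30% is in Sample Size Determination. That mismatch is a separate matter. With all 165 per arm analysed, power is 92%, the baseline used here.

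**2. Weight of one attendee.** Expected attendees are 0.03·165 ≈ 5 and 0.13·165 ≈ 21. One is worth 1/165 ≈ 0.6 points.

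**3. Effect of removal.** If a fraction a of attendees and b of non-attenders withdraw, the observed rate is

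r = p(1 − a) / [p(1 − a) + (1 − p)(1 − b)].

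Example, a = 0.20 and b = 0 in both arms: control 0.024/0.994 = 2.4%; intervention 0.104/0.974 = 10.7%; difference 8.3 points.

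| Assumed withdrawal | Control | Intervention | Difference (points) | Power |
|---|---|---|---|---|
| None | 3.0% | 13.0% | 10.0 | 92% |
| 5% of everyone | 3.0% | 13.0% | 10.0 | 91% |
| 5% of attendees, both arms | 2.9% | 12.4% | 9.6 | 91% |
| 10% of attendees, both arms | 2.7% | 11.9% | 9.2 | 89% |
| 20% of attendees, both arms | 2.4% | 10.7% | 8.3 | 86% |
| 20% of attendees, intervention arm only | 3.0% | 10.7% | 7.7 | 79% |
| 2% of attendees and 10% of non-attenders, both arms | 3.3% | 14.0% | 10.7 | 91% |

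Differences are taken before rounding the rates.

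**4. What is preserved.** The observed odds equal the true odds times (1 − a)/(1 − b). If a and b are the same in both arms, this factor cancels: the odds ratio stays at 4.83, and equal true rates stay equal. The risk ratio does move, for example from 4.33 to 4.42 at 20% of attendees in both arms.

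**5. What is not preserved if arms differ.** Suppose true attendance is 8% in both arms and 20% of attendees withdraw in the intervention arm only. The observed rates are 8.0% and 0.064/0.984 = 6.5%, a spurious difference of 1.5 points.

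**6. The test result.** From 5/165 versus 21/165 (chi-squared p = 0.001), removing 4 intervention attendees and no control attendees gives p = 0.007. Nine must be removed to reach p = 0.062; with Fisher's test, eight give p = 0.052.

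**The case against.** **The different offer does not show that withdrawal will differ.** This stands. Non-attenders hold the same right, with the same closing date and at least two weeks between the last debrief and any transfer. A reader might infer that deletion does depend on the outcome, or that people with outdated addresses never see the debrief. The protocol expects outdated contact details but says nothing about undelivered debriefs, so both remain inferences.

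**The direction is not fixed.** This also stands. It is tempting to say that the effect will shrink because attendees are the ones asked in person. But attendees chose to use the service, and if non-attenders withdraw more, the difference grows even with equal withdrawal across arms (last row of the table). In addition, attendees in both arms are debriefed in the same way, which gives no direct reason to expect their withdrawal to differ by arm. It does not rule it out.

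**Large effects need extreme rates.** Removing nine of 21 intervention attendees means 43% withdrawing there and none in the control arm. The study is described as minimal risk, and rates of 0 to 10% change little.

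**Sensitivity analyses and analysis sets belong in the SAP.** True in part, and a missing bounding analysis would not be a finding by itself. But the protocol states both the intention-to-treat label and the removal rule, and they conflict. It also limits what leaves the clinic before transfer to a count per arm, so an SAP can bound the result but cannot recover those participants' attendance.

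**Removal on request is the safeguard for waived consent.** Agreed; the right to withdraw data is not the error.

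**Conclusion.** The point holds as a conflict between stated rules plus an unquantified risk of bias. The unqualified intention-to-treat label is wrong as soon as one randomised participant withdraws data. Because the form and timing of the offer follow attendance, removal may be related to the primary outcome, in a direction the documents do not settle.

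At the planning rates, assumed withdrawal by 5 to 20% of attendees in both arms moves the difference from 10.0 to between 9.6 and 8.3 points and power from 92% to between 91% and 86%. Higher withdrawal among non-attenders moves the difference upward. A false effect requires withdrawal that also differs by arm. With no withdrawals there is no bias. The documents do not support saying that events will be selectively removed or that the estimate will be diluted.

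**What to change.** 1. In the Synopsis and Statistical Methods, replace the unqualified intention-to-treat statement with: all randomised participants except data withdrawals, analysed in the arm to which they were randomised.
2. Pre-specify a sensitivity analysis with all 165 per arm in the denominator, using the withdrawal counts per arm that the clinic already supplies, plus any withdrawals after transfer. Report four cases: all withdrawn attended; none attended; and the two opposite extremes (all attended in one arm and none in the other). As an invented example, with 2 control and 4 intervention withdrawals and 5 and 17 attendees observed, the extremes are (17 − 7)/165 = 6.1 points and (21 − 5)/165 = 9.7 points.
3. Optionally, and only if the ethics board agrees, ask the clinic to split the counts by attended yes or no (four aggregate numbers). This uses the outcome of people who withdrew their data, possibly in very small cells, so the first two changes should not depend on it.

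The first two changes cost a sentence and one short analysis, with no new data. As changes to the approved protocol they must be reported to the ethics board. The third needs the board's decision before extraction.
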